10.1.1.1.2 Sensitivity analysis

The sensitivity analyses shown below will be performed to determine the robustness of the analysis results. In the individual sensitivity analyses, as with the primary analysis, contrasts will be used to determine dose-response relationships and estimate treatment effects. However, this is not presented in graphs.

Multiple imputation (MI) will be performed 100 times.

1) MI - MMRM

Multiple imputed data will be generated in the MI procedures shown below. Each imputation data will be analyzed using the same MMRM model as that for the primary analysis, and the results of the analyses will be combined. Imputation will be performed for all available data obtained at each time point between Week 0 and Week 8 of the treatment period.

- (1) Non-monotone missing data will be imputed with a Markov Chain Monte Carlo (MCMC) method.
- (2) Monotone missing data will be imputed with an imputation formula generated using a regression model developed based on the data from all the groups.

2) Placebo MI - MMRM

Multiple imputed data will be generated in the MI procedures shown below. Each imputation data will be analyzed using the same MMRM model as that for the primary analysis, and the results of the analyses will be combined. Imputation will be performed for all available data obtained at each time point between Week 0 and Week 8 of the treatment period.

- (1) Non-monotone missing data will be imputed with an MCMC method.
- (2) Monotone missing data will be imputed with an imputation formula generated using a regression model developed based on the data from the placebo group.

10.1.2 Other assessment variables

10.1.2.1 Change from baseline in the mean NRS score

Summary statistics will be presented. A one-sample t-test will be used for comparisons within each group. A two-sample t-test will be used for comparisons between the placebo group and each of the MR13A9 0.25, 0.5, and $1.0 \mu g/kg$ groups.

Assessment time points: Weeks 1, 2, 3, 4, 5, 6, 7, and 8, Follow-up Weeks 1 and 2

10.1.2.2 Mean NRS score

Summary statistics will be presented. Means and standard deviations will be presented graphically.

Assessment time points: Weeks -1, 0, 1, 2, 3, 4, 5, 6, 7, and 8, Follow-up Weeks 1 and 2

Protocol No. MR13A9-4

Version: 1.0

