- h) Blood samples will be collected at Week 1 (before the first dialysis, at 5 minutes after administration of the week, before the second dialysis), Week 2 (before the first dialysis of the week), Week 4 (before the first dialysis, at 5 minutes after administration of the week, before the second dialysis), Week 7 (before the first dialysis, at 5 minutes and of the week, at least 1 hour after administration, before the second dialysis), and Week 8 (before the first dialysis of the week). At least 1 hour after administration at Week 7, blood sampling will be performed only in subjects from whom blood can be collected.

CONFIDENTIAL

Study Schedule (at the time of discontinuation)

	Treatment period	Follow	riod					
Visit	At discontinuation a)	Week 1 after discontinuation	Week 2 after discontinuation					
(weeks after initial dose)	discontinuation	discontinuation	aisc	continua	tion			
Visit	_		.,	 	r ·			
Day of the week	_	b)	Mon /Tue	Wed /Thu	Fri /Sat			
Study treatment								
NRS ^{c)}								
Shiratori's severity criteriac)								
Adverse events								
Concomitant medications/therapies								
Specific signs/symptoms ^{d)}	•	•	•					
Prohibited concomitant								
medications								
Hemodialysis conditions								
Skindex-16								
5-D itch scale	•							
PGIC	•							
Body weight ^{e)}								
12-lead ECG ^{e)}	•							
Vital signs ^{e)}								
Laboratory tests ^{e)}			•					
Postdialysis BUN								
Postdialysis weight								
Dependency assessment	● ^{e)}	•						
Serum pregnancy test ^{f)}	•							
Pharmacokinetics ^{e)}	•							

- a) Assessments and tests will be performed on the day of dialysis after discontinuation has been decided.
- b) Assessments at Week 1 after discontinuation will be performed on the same day of the week as the day of the assessments at discontinuation.
- c) To be recorded in the symptom diary once daily from the next day of the start date of the screening period until the visit day at Week 2 after discontinuation.
- d) Subjects will be examined for specific signs/symptoms at the time of discontinuation, at Week 1 after discontinuation, and at Week 2 after discontinuation.
- e) To be performed before dialysis.
- f) To be performed only in women of childbearing potential (within 1 year of their last menstrual period and who have not undergone total hysterectomy or bilateral total ovariectomy).

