- * Subjects discontinuing the study in the treatment period will undergo the assessments at discontinuation and enter into the follow-up period.

24. Appendices

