10.1 Primary Endpoint

The primary endpoint is the NRS score. The assessment time points and their evaluated time windows in the screening and treatment periods, and follow-up period are shown in Table 10.1-1 and Table 10.1-2, respectively.

Table 10.1-1 Assessment Time Points and Evaluated Time Windows in the Screening and Treatment Periods

Time point	Evaluated time window ^{a)}
Week -1	From Day -13 to Day -7
Week 0 (baseline)	From Day –6 to Day 1
Week 1	From Day 2 to Day 8
Week 2	From Day 9 to Day 15
Week 3	From Day 16 to Day 22
Week 4	From Day 23 to Day 29
Week 5	From Day 30 to Day 36
Week 6	From Day 37 to Day 43
Week 7	From Day 44 to Day 50
Week 8	From Day 51 to Day 57

a) The start date of the treatment period will be regarded as Day 1 and the previous day of the start date of the treatment period will be regarded as Day -1.

Statistical Analysis Plan Protocol No. MR13A9-4 Version: 1.0

Table 10.1-2 Assessment Time Points and Evaluated Time Windows in the Follow-up Period

Time point	Evaluated time window ^{a)}
Follow-up Week 1	From Day 1 to Day 7
Follow-up Week 2	From Day 8 to Day 14

a) The start date of the follow-up period (the date of treatment period completion or the next day of the date of discontinuation) will be regarded as Day 1.

The mean NRS score at each time point will be calculated as follows.

Mean NRS score at each time point = Sum of the NRS score observed during the evaluated time window ÷ Number of days when NRS score was observed during the evaluated time window

The change from baseline in the mean NRS score at each time point will be calculated as follows:

Change from baseline in the mean NRS score at each time point = Mean NRS score at each time point - Mean NRS score at baseline

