10.1.2.3 Responder rate in mean NRS score

The numbers and percentages of responders shown below will be presented. Fisher's exact test will be used for comparisons between the placebo group and each of the MR13A9 0.25, 0.5, and 1.0 μ g/kg groups. The percentages of responders will be presented graphically.

3 points responder: The change in the mean NRS score from baseline is -3

or less.

4 points responder: The change in the mean NRS score from baseline is -4

or less.

Assessment time points: Weeks 1, 2, 3, 4, 5, 6, 7, and 8, Follow-up Weeks 1

and 2

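### Follow-up Weeks 1 and 2 pool completers with early discontinuers, most of whom have no Week 8 value, so the step after Week 8 mixes a change of patients with any real off-drug change

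*SAP*

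**What the plan says.** - **One series.** SAP 10.1.2.2 lists "Assessment time points: Weeks -1, 0, 1, 2, 3, 4, 5, 6, 7, and 8, Follow-up Weeks 1 and 2" and adds "Means and standard deviations will be presented graphically". SAP 10.1.2.1 (one- and two-sample t-tests on change) and 10.1.2.3 (Fisher tests on 3- and 4-point responders) cover Weeks 1 to 8 and then Follow-up Weeks 1 and 2. For responders, "The percentages of responders will be presented graphically". SAP 10.2.1 applies the same summaries, t-tests and graph to the Shiratori score.
- **Personal clock.** The footnote to SAP Table 10.1-2 starts follow-up at "the date of treatment period completion or the next day of the date of discontinuation". Week 8 is a fixed study-day window, "From Day 51 to Day 57".
- **Stoppers stay in.** The Protocol's Study Schedule (at the time of discontinuation) says "Subjects discontinuing the study in the treatment period will undergo the assessments at discontinuation and enter into the follow-up period". Their diary runs "until the visit day at Week 2 after discontinuation". The FAS (SAP 4) does not remove subjects who stop during treatment.
- **Missing data.** Under SAP 6.2 a window with fewer than 4 diary days is missing. Nothing is imputed outside the sensitivity analyses of the primary variable.
- **Not stated.** None of these sections separates subjects by completion status, and SAP 10.1.2.3 gives no responder denominator.

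**The concern.** Someone reading the NRS or responder graph will use the step from Week 8 to Follow-up Week 1 to judge what happens when the drug is stopped. That is exactly where the set of subjects changes. Most early stoppers drop out of the series by Week 8, then can return at Follow-up Week 1 after anything from one dose to nearly eight weeks of exposure.

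The diary series are the only planned efficacy data after treatment: Skindex-16 and 5-D are analysed at Weeks 4 and 8 (SAP 10.2.2.1, 10.2.3.1), and PGIC at the final on-treatment assessment (SAP 10.2.4). Elsewhere the SAP gives early stoppers an on-treatment anchor. Laboratory tests, vital signs and body weight have an end-of-treatment time point beside Week 8 (SAP 12.2.1, 12.3.1). The diary endpoints have none.

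**Working it through.** **The plan's own figures.** The plan gives no figure for follow-up. Its Week 8 power does reproduce. With contrast (3, 1, -2, -2), differences 0, -0.6, -1.3, -1.3, SD 2.5 and 60 per group, the contrast value is -0.6 + 2.6 + 2.6 = 4.6, SE = 2.5 × √(18/60) = 1.369, noncentrality = 3.36 and power = 91.7% on 236 df. It does not depend on the follow-up windows.

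**Step 1: who is missing at Week 8.** Assume exits spread evenly over Days 2 to 56 (55 days) and a diary kept for 14 days after exit. At least 4 diary days are needed in Days 51 to 57.
- If only on-treatment diary days count, exit must be on Day 54 or later. Exits on Days 2 to 53 have no value: 52/55 = 95%.
- If post-discontinuation diary days also count, exit on Day 40 or later is enough. Exits on Days 2 to 39 have no value: 38/55 = 69%.

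The SAP does not say which reading applies.

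**Step 2: the artificial step in the mean.** Hold completers unchanged after stopping, so that any step is artificial. Let d be the stoppers' share of the follow-up sample, counting only those with usable diary data. Let m_c and m_d be the mean changes of completers and stoppers, and take the limiting case in which no stopper contributes at Week 8.

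Follow-up mean = (1 - d) × m_c + d × m_d, so step = d × (m_d - m_c).

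Take m_c = -3.4 (combined active groups of the non-Japanese 8-week phase II study, Protocol 7.6.2). The values of d and m_d are assumptions.

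| Stoppers' mean change | d = 5% | d = 10% | d = 20% |
|---|---|---|---|
| 0 | +0.17 | +0.34 | +0.68 |
| -1.9 (that study's placebo mean) | +0.08 | +0.15 | +0.30 |
| -3.4 (same as completers) | 0 | 0 | 0 |
| -4.4 | -0.05 | -0.10 | -0.20 |

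Positive means apparent worsening. SAP 10.1.2.2 plots the score itself, so these steps carry over to that graph only if stoppers and completers have the same baseline mean.

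The only related figures in the documents are treatment discontinued or interrupted due to events in the 2-week Japanese study (Protocol 1.3.2.2): 1/21 = 4.8%, 2/21 = 9.5% and 1/19 = 5.3% at 0.25, 0.5 and 1.0 μg/kg. Nothing in the documents supports 20%; it is an outer case.

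**Step 3: effect on the gap between arms.** Suppose stoppers average -1.0 in both arms and are 10% on drug and 5% on placebo.
- Drug: 0.90 × (-3.4) + 0.10 × (-1.0) = -3.16.
- Placebo: 0.95 × (-1.9) + 0.05 × (-1.0) = -1.855.
- The gap goes from 3.4 - 1.9 = 1.50 to 3.16 - 1.855 = 1.305. The arms appear to move closer.

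**Step 4: 3-point responders.** Assume normal changes with SD 2.34 (same study) and d = 10%. The completers' rate is Φ((-3 + 3.4)/2.34) = 56.8%. With the FAS denominator, missing counts as non-response, so Week 8 is 0.90 × 56.8% = 51.1%.

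| Stoppers' mean change | Observed-case denominator | FAS denominator |
|---|---|---|
| 0 | 56.8% to 52.1% | 51.1% to 52.1% |
| -1.9 | 56.8% to 54.3% | 51.1% to 54.3% |
| -3.4 | 56.8% to 56.8% | 51.1% to 56.8% |
| -4.4 | 56.8% to 58.4% | 51.1% to 58.4% |

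No completer relapses in any row, yet the percentage moves in all but one of the eight cases.

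**The case against.** The case against giving this weight is substantial, and most of it stands.

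- **Low stakes.** The objective is dose-response over 8 weeks of treatment, with no withdrawal or rebound objective. The primary MMRM uses Weeks 1 to 8, SAP 6.5.2 treats everything else as reference, and no planned test compares Week 8 with follow-up. This limits the point to a minor one.
- **Partly visible already.** Summary statistics include the number of subjects (SAP 3), and discontinuation is tabulated by group (SAP 7.2). A changing n can therefore be noticed. It still does not show how much of the step comes from the change of patients.
- **Not every stopper re-enters.** Those lost to follow-up or withdrawing may leave no usable diary, and some late stoppers may still have a Week 8 value. Both reduce the artificial step.
- **No known direction.** A reader might infer a certain false loss of effect that grows with drop-out. That needs stoppers to itch more than completers by a fixed amount, and the documents give no itch level for stoppers. Patients leaving for adverse events could be good responders, which reverses the sign.
- **No dose trend.** A reader might also infer an apparent dose-dependent rebound. The 2-week Japanese study shows no trend at the three doses used here; its high count was at 1.5 μg/kg, which this trial does not use.

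**Conclusion.** The structural defect holds. As written, the step from Week 8 to Follow-up Week 1 in the NRS and Shiratori series and in the responder graph compares different sets of patients. It cannot separate a change of patients from a real off-drug change, which is possible because all subjects stop study drug at that point.

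The direction is unknown. At 10% stoppers the artificial part of the mean step runs from +0.34 to -0.10 points over the cases shown, and is zero if stoppers match completers. If stoppers do worse and are more numerous on drug, the arms would look closer, not further apart. Nor must the responder percentage fall: that needs an observed-case denominator and stoppers who respond less often than completers, whereas with an FAS denominator it rises in every case shown.

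These sizes rest on assumed drop-out, exit timing and stopper means, because the documents give none for this trial. Severity is minor: the primary result and the sample size are untouched. It is worth correcting because these are the only planned post-treatment efficacy outputs and the correction is cheap.

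**What to change.** In SAP 10.1.2.1 to 10.1.2.3 and 10.2.1:

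1. Show Follow-up Weeks 1 and 2 in the same series as Week 8 only for subjects who completed the treatment period.
2. Add these subjects' within-subject change from Week 8 to each follow-up week, by group.
3. Tabulate the same windows after early discontinuation separately, as Post-discontinuation Weeks 1 and 2.
4. Print n at every plotted point, and state the responder denominator and how missing values count in it.
5. If the pooled between-group comparison is kept, label it as the first and second week after the end of treatment, whatever the length of treatment.

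With Week 8 and follow-up compared in the same completers, the change-of-patients part is zero by construction. The cost is SAP wording and a few table rows; discontinuation status is already collected, so no new data are needed. The downside is that the completer curve is conditional on completing, so its between-group reading is descriptive only.

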10.1.2.3 Responder rate in mean NRS score

The numbers and percentages of responders shown below will be presented. Fisher's exact test will be used for comparisons between the placebo group and each of the MR13A9 0.25, 0.5, and 1.0 μ g/kg groups. The percentages of responders will be presented graphically.

3 points responder: The change in the mean NRS score from baseline is -3

or less.

4 points responder: The change in the mean NRS score from baseline is -4

or less.

Assessment time points: Weeks 1, 2, 3, 4, 5, 6, 7, and 8, Follow-up Weeks 1

and 2

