Reported serious adverse events included the following: 2 events (encephalopathy and shunt stenosis) in 2 subjects in the 0.25 μ g/kg group, 8 events (abdominal distension, influenza, diverticulitis, dizziness, hyperglycaemia, cholecystitis, hypotension, and muscular weakness) in 4 subjects in the 0.5 μ g/kg group, and 1 event (dizziness) in 1 subject in the 1.5 μ g/kg group. Of these events, relationship to study treatment was not ruled out for 4 events (diverticulitis, dizziness, hypotension, and hyperglycaemia) in 3 subjects in the 0.5 μ g/kg group and 1 event (dizziness) in 1 subject in the 1.5 μ g/kg group. Study treatment was discontinued or interrupted due to 1 event in 1 subject in the 0.25 μ g/kg group, 2 events in

2 subjects in the 0.5 μ g/kg group, 1 event in 1 subject in the 1.0 μ g/kg group, and 17 events in 10 subjects in the 1.5 μ g/kg group. Dependency was assessed as being present in 2 subjects in the placebo group and 1 subject in the MR13A9 0.5 μ g/kg group.

In a non-Japanese phase II clinical study (CR845-CLIN2005 Part B), 65 hemodialysis patients with moderate to severe pruritus received intravenous doses of MR13A9 1.0 μ g/kg or placebo 3 times weekly for 2 weeks. With respect to efficacy, the primary endpoint of change in VAS (i.e., change from baseline in the mean VAS for the most intense itching at Week 2) (mean \pm standard deviation) was -33.1 ± 23.03 mm in the 1.0 μ g/kg group versus -21.5 ± 24.79 mm in the placebo group. With respect to safety, the incidence of adverse drug reactions was 9.4% (3/32 subjects) in the placebo group and 18.2% (6/33 subjects) in the 1.0 μ g/kg group. Commonly reported adverse drug reactions (in \geq 5% of subjects in the MR13A9 group) included dizziness, hypoaesthesia, and pruritus.

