7.5 Randomization and Blinding

7.5.1 Treatment Assignment

The person responsible for treatment assignment will prepare a treatment assignment table to assign subjects to MR13A9 0.25, 0.5, or 1.0 μ g/kg, or placebo at a ratio of 1:1:1:1.

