7.6 Sample Size

7.6.1 Sample size

This study will enroll 60 subjects for each MR13A9 dose group and the placebo group, 240 subjects in total.

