7.6.2 Rationale for the sample size

In the non-Japanese phase II clinical study (CR845-CLIN2101), the change from baseline in NRS score at Week 8 (mean \pm standard deviation) was -3.9 ± 2.48 , -2.8 ± 2.24 , and -3.4 ± 2.34 in the MR13A9 0.5 μ g/kg, 1.0 μ g/kg, and combined (CR845 all doses) groups, respectively, versus -1.9 ± 2.29 in the placebo group. The difference in the change from

baseline in NRS score (least squares mean \pm standard error) in each of the MR13A9 0.5 μ g/kg, 1.0 μ g/kg, and combined groups versus the placebo group was -1.8 ± 0.50 , -0.8 ± 0.52 , and -1.3 ± 0.41 , respectively.

For the present study, the MR13A9 0.5 and 1.0 μ g/kg groups were assumed to have a similar change in NRS score at Week 8 of the treatment period to that observed in the MR13A9 combined group in the non-Japanese phase II clinical study. The MR13A9 0.25 μ g/kg group, for which no efficacy results were obtained, was assumed to have about half the change in NRS score assumed above. The mean difference in NRS score between each of the MR13A9 0.25, 0.5, and 1.0 μ g/kg groups and the placebo group was assumed to be -0.6, -1.3, and -1.3, respectively, with a common standard deviation of 2.5. When the dose-response relationship for the MR13A9 0.25, 0.5, and 1.0 μ g/kg groups was evaluated using the contrast patterns shown in "13.5.2.1.1 Primary analysis," with a two-sided significance level of 5% and a sample size of 60 subjects per group, a contrast pattern of 3, 1, -2, -2 (placebo, 0.25, 0.5, 1.0 μ g/kg) produced a statistical power of 91.7%. Statistical power is more than 80% when the MR13A9 0.5 or 1.0 μ g/kg group (60 subjects per groups) was compared with the placebo group.

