All statistical tests will be performed using a two-sided significance level of 5%; however, a two-sided significance level of 15% will be used for the analysis of between-group imbalance. Summary statistics will be presented as the number of subjects, mean, standard deviation, minimum, median, maximum, and quartile. Unless otherwise specified, data will be tabulated by group and by time point. Week 0 will be the baseline.

SAS System Release 9.4 for Windows (SAS Institute Inc.) will be used to conduct the analysis.

4. Analysis Sets

The analysis sets are defined as follows. When the full analysis set (FAS) and the per protocol set (PPS) are used as analysis sets, analyses will be performed based on the treatment group to which each subject has been allocated. When the safety set (SS) and the pharmacokinetic analysis set (PKS) are used as analysis sets, analyses will be performed based on the treatment group in which each subject has been actually treated.

- FAS: Population of subjects, excluding the following subjects: subjects with GCP violations, untreated subjects, discontinued subjects before entry to the treatment period, some of the ineligible subjects, and subjects with no available mean NRS score at baseline (Week 0)
- PPS: Population of subjects, excluding the following subjects from the FAS: ineligible subjects, discontinued subjects, deviators, and subjects with broken emergency key codes, as the subjects to be excluded from the PPS

Statistical Analysis Plan	Protocol No. MR13A9-4
	Version: 1.0

- SS: Population of subjects, excluding the following subjects: subjects with GCP violations, untreated subjects, and discontinued subjects before entry to the treatment period
- PKS: Population of subjects, excluding the following subjects from the SS: subjects with no available plasma drug concentration data

Correspondence of the analysis items and the analysis sets is shown in Table 4-1.

Table 4-1 Analysis Items and Analysis Sets

Endpoints	Analysis items	Analysis sets
Demographic and other baseline	Subject demographics	FAS, PPS, SS, PKS
characteristics	Other	SS
Treatment compliance	All items	FAS, SS
Efficacy	Primary variable (primary analysis)	FAS (primary analysis set), PPS
	Other	FAS
Pharmacokinetics	All items	PKS
Safety	All items	SS

5. Analysis Groups

- MR13A9 0.25 μg/kg group: Subjects allocated to or treated with MR13A9 0.25 μg/kg
- MR13A9 0.5 μg/kg group: Subjects allocated to or treated with MR13A9 0.5 μg/kg

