6.2 Handling of Dropouts or Missing Data

When there is a lack in the data used for analysis, all items other than the following items will be handled as missing values, and no imputation by statistical methods will be performed. Sensitivity analyses of the primary variable will use multiple imputation. The details are shown in "10.1.1.1.2 Sensitivity analysis."

If the number of days of observation during the evaluation period is less than 4 days as of the time of calculation of the mean NRS score and the mean itch score based on the Shiratori's severity criteria at each time point, the score at that time point will be handled as missing.

If the overall score or the subscores (symptoms score, emotions score, and functioning score) of the Skindex-16 or the responses to the questions used for calculation of the total score of 5-D Itch Scale are missing, the score will be handled as missing.

Any plasma drug concentration below the lower limit of quantification (BLQ) will be treated as 0.

Any BLQ values observed in laboratory test values will be handled as the values of the quantification limit.

In the calculation of geometric mean and geometric CV, values of 0 before log-transformation will be handled as missing values.

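### The NRS responder analysis drops subjects without a valid weekly mean and, unlike the NRS change score, has no companion analysis that accounts for drop-out

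*SAP*

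**What the plan says.** SAP 10.1.2.3 defines a responder only by the change in weekly mean NRS (a fall of at least 3, or at least 4, points). For Weeks 1 to 8 and Follow-up Weeks 1 and 2 it states: "The numbers and percentages of responders shown below will be presented". Each dose is compared with placebo by Fisher's exact test. The section names no denominator and no rule for a subject who has no weekly mean. Table 4-1 assigns the analysis to the FAS.

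The rule for missing data is in SAP 6.2. Fewer than 4 diary days in a window makes that week's mean missing. Data lacking for items outside a short list of exceptions "will be handled as missing values, and no imputation by statistical methods will be performed". Responder status is not among the exceptions. Multiple imputation is reserved for the primary variable's sensitivity analyses, where SAP 10.1.1.1.2 says: "Multiple imputation (MI) will be performed 100 times".

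SAP section 2 says the responder rate was added so that the evaluation matches the viewpoint of the US phase II study (CLIN2101). SAP 6.5.2 gives every item other than the primary variable reference status.

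**The concern.** A responder percentage is a count divided by a number of subjects. If subjects who stop leave the divisor, the percentage rises whenever those lost were not responding. Protocol 4.3.1 lists adverse events and lack of efficacy among the reasons to stop, and many such subjects would not be counted as treatment successes. When the loss differs between arms, the comparison mixes the treatment effect with the pattern of stopping.

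The NRS change score is protected against this by an MMRM on all available Week 1 to 8 data, with two multiple-imputation sensitivity analyses. The responder rate has no counterpart. What is at stake is how far a reader can trust the responder percentages and their p-values, not the trial's primary result.

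**Working it through.** **Inputs from the documents.** Sample size: "This study will enroll 60 subjects for each MR13A9 dose group and the placebo group, 240 subjects in total", allocated "at a ratio of 1:1:1:1". Tests are two-sided at 5% (SAP section 3). Placebo change at Week 8 in CLIN2101: mean -1.9, SD 2.29 (Protocol 7.6.2). The documents state no responder rate and no drop-out rate.

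**The plan's own figure.** Protocol 7.6.2 gives 91.7% power for contrast (3, 1, -2, -2), where the difference from placebo "was assumed to be -0.6, -1.3, and -1.3, respectively, with a common standard deviation of 2.5". The contrast value is |1(-0.6) - 2(-1.3) - 2(-1.3)| = 4.6. Its standard error is 2.5 × √(18/60) = 1.369, so the noncentrality is 4.6/1.369 = 3.36. With 236 degrees of freedom the power is 91.7%, as stated. This figure does not depend on the responder rule.

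**What happens to a subject who stops.** With no valid weekly mean there is no change score, so neither responder definition can be evaluated. Counting that subject as a non-responder would be an imputation that SAP 6.2 does not provide for. The subject therefore leaves that week's percentage and test. Eligibility is judged week by week: someone who stops in Week 5 still counts in earlier weeks. Because the diary continues after discontinuation and follow-up windows start the day after it (Table 10.1-2), the same subject can be absent at Week 8 and present at Follow-up Week 1.

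**Size when there is no true difference (assumed).** Assumptions: 60 FAS subjects per arm, true responder rate 35% in both, and every lost subject a non-responder. A normal approximation to the CLIN2101 placebo data gives Φ((-3 + 1.9)/2.29) = 31.5% for the 3-point definition, so 35% is of a plausible order. With x and y responders and d₁ and d₂ subjects lost, the rejection rate is the sum over all x and y of Bin(x; 60, 0.35) × Bin(y; 60, 0.35), taken where Fisher's p for x/(60 - d₁) against y/(60 - d₂) is at most 0.05. At the expected count, x = y = 0.35 × 60 = 21.

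| Lost (arm A, arm B) | Percentages at 21 responders each | Spurious gap | Fisher rejects |
|---|---|---|---|
| 0, 0 | 35.0% v 35.0% | 0 | 3.1% |
| 6, 3 | 21/54 = 38.9% v 21/57 = 36.8% | 2.0 points | 4.9% |
| 9, 3 | 21/51 = 41.2% v 36.8% | 4.3 points | 6.9% |
| 12, 3 | 21/48 = 43.8% v 36.8% | 6.9 points | 10.8% |

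If 15% against 5% are lost but loss is unrelated to response, the rejection rate is 4.1%.

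**Size when there is a difference (assumed).** Take 24/60 against 15/60: 15 points, p = 0.118. Losing 6 and 3 non-responders gives 24/54 against 15/57: 18.1 points, p = 0.04998. If instead 2 of the 6 and 1 of the 3 lost were responders, the result is 22/54 against 14/57: 16.2 points, p = 0.104, close to the full-data answer.

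**The case against.** **The denominator is inferred.** SAP 10.1.2.3 states none, and Table 4-1 assigns the analysis to the FAS, so an all-FAS percentage is not literally ruled out. That stands as a caution. But reaching such a percentage means treating missing as non-response, which SAP 6.2 does not allow for, so the observed-case reading is the natural one.

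**A reader might infer that the bias favours the higher doses.** The documents do not support this. In MR13A9-3 (Protocol 1.3.2.2), treatment was discontinued or interrupted for "and 17 events in 10 subjects in the 1.5" μg/kg group, a dose not studied here. At the doses in this trial the counts were 1/21 (4.8%) at 0.25, 2/21 (9.5%) at 0.5 and 1/19 (5.3%) at 1.0 μg/kg. That shows no gradient, mixes stopping with interruption, and covers 2 weeks. Stopping for lack of efficacy could remove more placebo subjects and reverse the bias, and subjects who stop for adverse events may have been itch responders.

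**A reader might also infer that this is the only observed-case NRS result.** It is not. The t-tests in SAP 10.1.2.1 follow the same rule. The difference is that the change score also has an MMRM and imputation, and the responder rate does not.

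**The illustration is a worst case.** This stands: it assumes that all lost subjects are non-responders. At 6 against 3 lost, the rejection rate stays below the nominal 5%.

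**Consequence and comparability.** The analysis is a reference item, and nothing in the documents says it will be the headline result. How CLIN2101 handled missing responders is not shown, so replacing the observed-case result could harm the comparison it was added for. This is a good reason to add an analysis and not to substitute one.

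**Conclusion.** The point holds as a minor one. SAP 6.2 and 10.1.2.3 together produce an observed-case responder rate with no analysis that accounts for drop-out. The bias is conditional on unequal loss of non-responders, and its direction by arm is unknown. Under the stated assumptions the spurious gap is about 2 to 7 points, and the rejection rate goes from 3.1% to between 4.9% and 10.8%. With equal loss, or with loss unrelated to response, there is little or no distortion. The primary analysis does not use responder status and is unaffected.

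**What to change.** In SAP 10.1.2.3, for Weeks 1 to 8, add a responder analysis with every FAS subject in the denominator, by one of two routes:

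- count a missing weekly mean as non-response and keep Fisher's exact test; or
- derive responder status in each of the 100 imputed data sets of SAP 10.1.1.1.2 and combine the risk differences by Rubin's rules, with the matching test and confidence interval. Fisher p-values have no standard pooling, so the test must be named.

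Amend SAP 6.2 to list this as an exception. Keep the observed-case result for comparability with CLIN2101, state its denominator, and report the number missing per arm and week.

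The cost is a few sentences and a short program, with no new data. Percentages will be slightly lower. The non-responder rule also counts isolated diary lapses as failures and can err the other way: in the mixed-loss example above it gives 22/60 against 14/60, or 13.3 points against the full-data 15.
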